## 7.0 STATISTICAL ANALYSIS

Starting from this section, this statistical analysis plan will only focus on Phase 1b part of the study where patients were enrolled.

### 7.1 Patient Disposition

The summary for subject disposition will include number of subjects enrolled in the dose escalation phases, number of subjects in each study population, number of subjects who discontinue from study treatment and reason for treatment discontinuation, and number of subjects who discontinue from study and reasons for study discontinuation.

All patients in enrolled population will be included in the summary table, additional summary tables will be generated for HNSCC and CRC enrolled population separately. All disposition data will be presented in a data listing.

### 7.2 Protocol Deviations

Protocol deviations will be classified as significant/major or non-significant/minor and grouped into categories. A protocol deviation that affects primary efficacy and safety assessments (as applicable), the safety or mental integrity of a subject, or the scientific value of the trial is considered as significant protocol deviation.

The number and percentage of patients with significant protocol deviations in each category will be summarized. Significant protocol deviations will be provided in listings.

### 7.3 Study Population

#### 7.3.1 Demographic and Other Baseline Disease Characteristics

Demographic and baseline characteristics will be summarized and listed for the safety population, additional summary tables will be generated for HNSCC and CRC safety population separately.

Demographic variables include the following:

- Age
- Age categorization I (< 65,  $\geq$  65 years)
- Age categorization II (<65,  $\geq$  65 and < 75,  $\geq$  75 years)
- Age categorization III (<65,  $\geq$  65 and < 75,  $\geq$  75 and <85,  $\geq$  85 years)
- Sex
- Ethnicity (Hispanic or Latino, not Hispanic or Latino)
- Race (White, Black or African American, Asian, American Indian or Alaska Native, Native Hawaiian or Other Pacific Islander, and Unknown, Race not reported)

Baseline characteristics include:

- Height (cm)
- Weight (kg)
- Body mass index (BMI) (kg/m^2)
- ECOG status

### 7.3.2      **Cancer History and Prior Cancer Treatment**

The following prior cancer history and cancer treatment history will be summarized and listed for HNSCC and CRC safety population separately.

**Table 4:                    Cancer History and Prior Cancer Treatment**

Cancer Type	Parameters
All	
 
• Time from initial primary cancer diagnosis to first dose of NKTR-255 (months)
 
• Stage at initial diagnosis
 
• Stage at most recent recurrence
 
• Current status
 
• Number of lines of prior systemic cancer therapy
 
• Time since start of most recent line of systemic cancer therapy
 
• Best response of most recent line of systemic cancer therapy
 
• Sites of metastasis
 
• EGFR Mutational Status
 
• Prior EGFR experience
 
• Prior PD-1/L1 experience
 

HNSCC	
 
• Histological type
 
• Human papillomavirus infection (HPV) status
 
• Epstein-Barr virus (EBV) status
 
• P16 status
 
• PD-L1 combined positive score (CPS)
 

CRC	
 
• History of brain metastases
 
• Mutational status (BRAF status, NRAS/KRAS Status)
 
• MSI status
 

### **7.3.3 Surgical History and Prior Radiotherapy**

The number and percent of patients who had prior cancer-related surgery will be summarized by type of surgery.

The number and percent of patients who had prior radiotherapy will be summarized by site of radiotherapy.

All prior radiotherapy and cancer related surgery history will be listed.

### **7.3.4 Medical History**

Medical history collected at screening will be coded by the Medical Dictionary for Regulatory Activities (MedDRA) and summarized by system organ class (SOC) and preferred term (PT) for HNSCC and CRC safety population separately. For summary tables, patient will be counted only once within each SOC and PT. All medical history will also be provided in a listing

## **7.4 Treatments and Medications**

### **7.4.1 Prior and Concomitant Medications**

Prior and concomitant medications will be coded by the World Health Organization Drug Dictionary Enhanced (WHODrug) using Anatomical Therapeutic Chemical (ATC) level 2 term and preferred Term (PT). The number and percentage of subjects who have received each prior medication and who have received each concomitant medication will be summarized by ATC level 2 term and PT. Subjects will be counted only once under each ATC level 2 term and preferred term.

Prior or concomitant medications are defined in Section 6.6.1 and will be classified based on recorded or imputed start dates of medication taking with rules specified in and Sections 6.4.

All prior and concomitant medications will be listed.

### **7.4.2 Subsequent Anti-Cancer Therapy**

Subsequent cancer therapy will be coded by the WHODrug using ATC level 2 term and PT. The number and percentage of subjects who have subsequent cancer therapy will be summarized by ATC level 2 term and PT. Subjects will be counted only once under each ATC level 2 term and preferred term.

All subsequent cancer therapy will be listed.

### **7.4.3 Study Drug Exposure and Dose Modification**

The number and percentage of subjects with at least one dose delays, dose reductions, and dose interruptions, and the reasons will be summarized respectively for HNSCC and CRC safety population.

The following variables will also be summarized for NKTR-255 and cetuximab respectively for HNSCC and CRC safety population:

- Exposure duration (days): Date of last administration – date of first administration +1, regardless of any delay of dosing between the first and the last dose.
- Actual number of infusions: Total number of infusions for which the patient received non-zero doses.
- Planned number of infusions: The cycle number for which the patient received last non-zero doses.
- Cumulative dose (ug): The summation of actual dose a patient received across all cycles. The units ug/kg used for NKTR-255 and mg/m^2 for cetuximab.
- Average dose per infusion (ug): Cumulative dose / Actual number of infusions.

All study exposure summary data will be presented in a data listing.

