## 1.0 STUDY SYNOPSIS

Name of Sponsor:	Nektar Therapeutics
Name of Finished Products:	NKTR-255 Drug Product Erbitux®
Name of Active Ingredients:	NKTR-255 Drug Substance Cetuximab
Title of Study:	A Phase 1b/2, Open-label, Multicenter, Dose Escalation, and Dose Expansion Study of NKTR-255 Monotherapy or in Combination with Cetuximab as a Salvage Regimen for Solid Tumors
Duration of Treatment:	In Phase 1b, patients will receive an intravenous (IV) loading dose of cetuximab alone, followed 7 days later by the first combination treatment of IV cetuximab and IV NKTR-255 on Cycle 1 Day 1 (C1D1). Thereafter, IV NKTR-255 will be given in 21-day cycles in combination with weekly IV cetuximab.  In Phase 2, patients will receive either NKTR-255 in combination with cetuximab in 21-day cycles or will receive NKTR-255 monotherapy in 21-day cycles. Patients who achieve optimal response in the NKTR-255 in combination with cetuximab cohorts may move to NKTR-255 monotherapy maintenance given in 28-day cycles.  Patients will remain on treatment until meeting one of the criteria for discontinuation of treatment in Section 5.2.3.1.
Phase of Development:	Phase 1b/2
Objectives:	
The primary objectives are:
 
Phase 1b (Dose Escalation):
 
 
To evaluate the safety and tolerability, as well as define the maximum tolerated dose (MTD) and/or recommended Phase 2 dose (RP2D), of NKTR-255 in combination with cetuximab in relapsed or refractory (R/R) head and neck squamous cell carcinoma (HNSCC) or colorectal carcinoma (CRC)
 
 
Phase 2 (Dose Expansion):
 
 
To evaluate the safety and tolerability of NKTR-255 monotherapy and NKTR-255 in combination with cetuximab in R/R HNSCC, CRC. CCI [REDACTED]
 
To evaluate the efficacy of NKTR-255 in combination with cetuximab in R/R HNSCC or CRC by assessing the objective response rate (ORR) by Response Evaluation Criteria in Solid Tumors (RECIST) version 1.1
 
 
The secondary objectives are:
 
 
To evaluate the efficacy of NKTR-255 monotherapy in R/R [REDACTED] by assessing the ORR by RECIST 1.1
 
To evaluate the efficacy of NKTR-255 in combination with cetuximab and NKTR-255 monotherapy by assessing progression-free survival (PFS) and overall survival (OS)
 

CCI

CCI	

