**Table 1: Schedule of Visits and Assessments – Phase 1b (CRC and HNSCC; NKTR-255 Dose Escalation) (Contd)**

Event a	Screening Period	Treatment Period																		Post-treatment Period									
		Run-in (1 week) Day			Cycle 1 (21-day cycle) Day						Cycle 2 (21-day cycle) Day						Cycle 3 (21-day cycle) Day			Cycle 4+ (21-day cycles) Day									
		≤ 28d prior to Day 1 of Run-in Period			-7	-6	-4	1	2	3	4	5	8	10	15	1	2	3	4	8	10	15	1	4	8	15	EOT b	60-day Follow-up c	Survival Follow-up c
Windows (days)		+1			+1										+1							+1			+1		+7	±14	Every 3 months ±14 days
Study Drug Administration																													
NKTR-255 administration u						X									X							X			X				
Cetuximab administration v			X			X				X	X	X				X		X	X	X	X	X	X	X					
Concomitant medications review	Continuous from time of ICF until 60 days after last study treatment dose																												
Efficacy Assessments																													
Tumor measurements and RECIST 1.1 and irRECIST response assessments w	Tumor assessments at Screening and every 9 weeks from C1D1 + 7 days until patients meet one of the criteria for discontinuation of treatment in Section 5.2.3.1.																												
Subsequent therapy/survival/secondary malignancy information																							X	X	X				

AE = adverse event;  $\beta$ -HCG = beta subunit of human chorionic gonadotropin; CK = creatine kinase; CnDn = Cycle n Day n; CRC = colorectal cancer; d = day; ECG = electrocardiogram; EBV = Epstein-Barr virus; ECOG = Eastern Cooperative Oncology Group; EOI = end of infusion; EOT = end of treatment; HBV = hepatitis B virus; HCV = hepatitis C virus; HIV = human immunodeficiency virus; HNSCC = head and neck squamous cell carcinoma; HPV = human papillomavirus; ICF = informed consent form; irRECIST = immune-related RECIST 1.1; IV = intravenous(ly); LVEF = left ventricular ejection fraction; MRI = magnetic resonance imaging; MUGA = multigated acquisition; PaO2 = oxygen saturation; CCI [REDACTED] PK = pharmacokinetic(s); PT = prothrombin time; PTT = partial thromboplastin time; q21d = every 21 days; q3 = every 3; RECIST = Response Evaluation Criteria In Solid Tumors; T3 = triiodothyronine; T4 = thyroxine; TSH = thyroid-stimulating hormone; WCBP = women of childbearing potential

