- k. On C1D1 and C2D1, ECGs are required predose and end of NKTR-255 infusion. All other timepoints, collect ECGs predose. Patients must be resting quietly in the supine position for  $\geq$  5 minutes prior to collection of 12-lead ECG.
- l. For women of childbearing potential (WCBP) only, perform a serum beta subunit of human chorionic gonadotropin ( $\beta$ -HCG) pregnancy test at Screening within 10 to 14 days prior to dosing, and urine or serum pregnancy test within 24 hours prior to day of dosing NKTR-255 on C1D1. In subsequent cycles, perform urine or serum test once each dosing cycle. A negative result is required prior to dosing. Pregnancy testing is not required for women who are postmenopausal for at least 1 year, or surgically sterile for at least 3 months prior to signing the ICF.

- m. See [Appendix 4](#). Central safety laboratory results must be used to determine patient eligibility, with the exception that pregnancy tests are done locally (see Section 7.11); thereafter, central laboratory samples must be obtained prior to each cycle. If local laboratory results are used for retreatment decisions due to timing issues (eg, predose, treatment-related AE management, dose delays, etc.), duplicate central safety laboratory tests must be submitted to the central laboratory.
- n. Tests include free or total triiodothyronine (T3) reflex testing if TSH is abnormal.
- o. Refer to the Laboratory Manual for sample processing. See [Table 7](#) for detailed sampling timepoints.

- u. NKTR-255 will be administered q21d starting C1D1.
- v. Cetuximab will be administered at the recommended dose according to the current local prescribing information, ie, IV weekly. A loading dose of 400 mg/m^2 IV is given as an initial dose, then weekly doses of 250 mg/m^2 IV. On days that NKTR-255 and cetuximab are both dosed, cetuximab should be administered first, [CCI](#)
- w. Patients will remain on treatment until meeting one of the criteria for discontinuation of treatment in Section [5.2.3.1](#).

CCI

CCI

CCJ

CCI

CCI

CCI

CCI

CCI

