Eligible patients will receive cetuximab 400  $\text{mg}/\text{m}^2$  IV as a loading dose during the study run-in period (Day -7). Thereafter, cetuximab 250  $\text{mg}/\text{m}^2$  IV will be administered weekly and NKTR-255 will be administered q21d. The DLT window is 21 days after the first dose of NKTR-255. Patients who achieve optimal response (partial response [PR] or complete response [CR] as determined by RECIST 1.1) after at least 1 tumor assessment, as determined by the Investigator and in consultation with the Medical Monitor, will be given the option to continue treatment with NKTR-255 as single agent for maintenance every 28 days (q28d) at the same dose as the patient's originally assigned dose.

CCI [REDACTED]

The logo consists of the letters 'CCI' in a large, bold, red sans-serif font. The letters are slightly overlapping, with 'C' on the left, 'C' in the middle, and 'I' on the right. The background is a solid black rectangle.

- Intermediate doses may be evaluated.
- No intra-patient dose escalation will be allowed.
- Enrollment into a new dose level with an escalating dose of NKTR-255 cannot begin until the DLT window has closed for at least 3 patients in the prior dose level. The DLT window is 21 days after the first dose of NKTR-255.
- The SRC will assess safety before opening dose escalation to the next level.
- The Sponsor's decision to declare the RP2D of NKTR-255 can occur at any given dose level based on safety, PK or CCI ██████ effects without reaching the MTD.
- Data from a minimum of 6 evaluable patients are required to define the RP2D.
- Dose reduction of NKTR-255 is not allowed during dose escalation within the DLT window. Outside of the DLT window in the dose escalation phase, and during dose expansion, dose levels of NKTR-255 may be reduced depending on the severity, duration, and frequency of toxicities observed at the previous dose level tested (the dose level may be de-escalated in order to characterize RP2D for a specific dose).
- The cetuximab dose may be reduced or adjusted based on review of available safety and tolerability data. Dose adjustment or discontinuation for cetuximab may be required based on emerging toxicities, and should follow the guidelines specified in this protocol and in the current local prescribing information for cetuximab.

CCI

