## 6.6 Definitions

### Run-in period:

Eligible patients on combination therapy will receive cetuximab 400mg/m^2 IV as a loading dose during the study run-in period (Day -7). The run-in period therefore starts from the time the patient receives cetuximab and ends when the patient receives combination treatment of NKTR-255 +cetuximab.

**Study drug or study treatment:** Study drug or study treatment refers to NKTR-255 or cetuximab.

**Study day:** Study Day 1 (C1D1) is the first day that the combination treatment of NKTR-255 +cetuximab begins.

**Baseline:** Unless otherwise specified, the baseline value for each variable is the last non-missing value collected at the time (if collected) closest to, but prior to, the start of NKTR-255 administration. For triplicate ECG data, the record with three non-missing value will be considered as non-missing. If multiple measurements occur on the same day at the same time, or on the same day but the time is not available, the average of the measurements (for continuous data) will be considered the baseline value. When dosing times and/or observation times are not collected, it is assumed that protocol planned in-office assessments obtained on the day of the first dose of study drug are prior to administration of the first dose of study drug and therefore considered baseline values.

**Last known alive date:** The date of last known alive date will be derived for patients unknown to have died or known alive at the analysis cut-off by using following dates:

- Patient assessment dates (blood draws **CCI** [REDACTED], vital signs, performance status, ECG, tumor assessments, ECOG, or tumor biopsy dates)
- Start and end dates of anti-cancer therapies administered after study treatment discontinuation
- AE start or end date
- Concomitant medication start or end dates
- Last date of contact collected on the 'Survival follow-up' eCRF (do not use date of survival follow-up assessment unless status is 'alive')
- Study treatment start or end date
- Date of discontinuation for study participation on disposition eCRF pages (do not use if reason for discontinuation is lost to follow-up)

Only dates associated with actual examinations of the patient will be used in the derivation. Dates associated with a technical operation unrelated to patient status such as the date a blood sample was processed will not be used.

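### SAP 7.4.3 counts planned infusions by cycle for both drugs, so the row for weekly cetuximab comes out about three-fold too low

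*SAP*

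**What the plan says.** SAP 7.4.3 gives a single list of exposure variables, introduced by "The following variables will also be summarized for NKTR-255 and cetuximab respectively". Two adjacent items are "Actual number of infusions: Total number of infusions for which the patient received non-zero doses" and "Planned number of infusions: The cycle number for which the patient received last non-zero doses". The visible section has no separate counting rule for cetuximab, although the cumulative-dose item does distinguish the two drugs by unit.

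The dosing schedules differ. The protocol synopsis says of Phase 1b: "Thereafter, IV NKTR-255 will be given in 21-day cycles in combination with weekly IV cetuximab". Protocol 5.1.1 says that, after the loading dose on Day -7, cetuximab "will be administered weekly and NKTR-255 will be administered q21d". Footnote v to protocol Table 1 agrees: "Cetuximab will be administered at the recommended dose according to the current local prescribing information, ie, IV weekly". SAP 6.6 puts the loading dose in a run-in before Cycle 1: "The run-in period therefore starts from the time the patient receives cetuximab and ends when the patient receives combination treatment".

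**The concern.** A cycle number equals a count of scheduled infusions only for a drug given once per cycle. NKTR-255 meets that condition. Cetuximab has three weekly infusions in each 21-day cycle, plus a loading infusion that belongs to no numbered cycle and so cannot be captured by a cycle number at all.

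Planned and actual infusions sit side by side so that a reader can see how much of the scheduled treatment was delivered. Under this rule a fully compliant patient appears to have received several times the planned number of cetuximab infusions. A real shortfall can also read as a surplus: a patient last dosed on Cycle 2 Day 15 who received only 4 of the 7 scheduled infusions would show 4 actual against 2 planned. Average dose per infusion does not reveal the omission, because it divides by actual infusions.

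**Working it through.** The plan states no planned-infusion figure, so there is nothing to reproduce first. The check is a direct count from the schedule.

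**Inputs**
- NKTR-255: one infusion per 21-day cycle from Cycle 1 Day 1 (protocol Table 1, footnote u).
- Cetuximab: weekly, so 21/7 = 3 infusions per cycle, on Days 1, 8 and 15 (protocol synopsis, 5.1.1, Table 1 footnote v).
- Cetuximab loading dose: one infusion on Day -7 (protocol 5.1.1; SAP 6.6).
- SAP planned number: k, the cycle of the last non-zero dose (SAP 7.4.3).

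As a cross-check, the "Cetuximab administration" row of protocol Table 1 carries 13 marks, which fits 1 + 3 × 4 (a loading dose and four cycle blocks). The column headings are damaged in the text available, so assigning marks to days is inference. The count below rests on the prose.

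**NKTR-255.** Scheduled = k and SAP planned = k, so the ratio is 1.0 in every cycle.

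**Cetuximab.** Let the last dose be the first, second or third weekly dose (Day 1, 8 or 15) of cycle k.
- With the loading dose: 1 + 3(k-1) + (1, 2 or 3) = 3k-1, 3k or 3k+1. Ratio to k: 3 - 1/k, 3 or 3 + 1/k.
- Without it: 3(k-1) + (1, 2 or 3) = 3k-2, 3k-1 or 3k. Ratio to k: 3 - 2/k, 3 - 1/k or 3.

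| k (SAP planned) | Scheduled with loading dose, last dose Day 1 / 8 / 15 | Ratio | Scheduled without it | Ratio |
|---|---|---|---|---|
| 1 | 2 / 3 / 4 | 2.0 to 4.0 | 1 / 2 / 3 | 1.0 to 3.0 |
| 2 | 5 / 6 / 7 | 2.5 to 3.5 | 4 / 5 / 6 | 2.0 to 3.0 |
| 6 | 17 / 18 / 19 | 2.83 to 3.17 | 16 / 17 / 18 | 2.67 to 3.00 |
| 12 | 35 / 36 / 37 | 2.92 to 3.08 | 34 / 35 / 36 | 2.83 to 3.00 |

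Both ranges tend to 3. The four-fold end occurs only with a last dose on Cycle 1 Day 15 and the loading dose counted. The only case with no error is a last dose on Cycle 1 Day 1 with the loading dose left out.

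**Compliant patient, two complete cycles.** Scheduled and received: 1 + 3 + 3 = 7, against SAP planned 2, ratio 7/2 = 3.5. If the loading dose is left out of both counts: 6 against 2, ratio 3.0.

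**Can a reader recover the right count?** Exposure duration for that patient is 7 + 21 + 14 + 1 = 43 days, and (43 - 1)/7 + 1 = 42/7 + 1 = 7. So yes, if no dose was delayed. With delays this no longer works cleanly.

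**Off the nominal schedule.** Four-fold is not a firm upper bound. Assume that weekly cetuximab continued through a 2-week NKTR-255 delay between Cycles 1 and 2, which the visible text does not state. Two complete cycles would then hold 1 + 3 + 2 + 3 = 9 infusions against 2, ratio 4.5.

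**The case against.** The strongest reply is that nothing depends on this row. Average dose per infusion uses actual infusions, no relative dose intensity is defined in the visible text, and SAP 7.4.3 summarizes delays, reductions and interruptions, with reasons, on their own lines. Only Phase 1b enrolled, with about 30 patients planned, and 7 against 2 for a weekly drug would strike most readers as a slip in the definition. That stands, and it is why the point is minor. It does not make the tabulated number right.

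A second reply is that the treatment of the loading dose is open. The SAP does not say whether planned infusions include it. The actual-infusions item has no exclusion, so inclusion is the natural reading, but the cumulative-dose item sums over cycles and the loading dose precedes Cycle 1. This is fair, and both ranges are therefore given. Leaving the loading dose out does not rescue the rule: the ratio is still 2.0 to 3.0 in Cycle 2 and approaches 3 later.

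A third reply is that infusions given during an NKTR-255 delay, or after NKTR-255 stops, are hard to call planned. Protocol 5.2.3.1 leaves continuation on cetuximab alone to the investigator, and the visible text does not set out the weekly schedule for either case. This is a reason to write a convention down. Whatever is chosen, both rows must use it, or a compliant patient will again show more infusions than planned.

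**Conclusion.** The concern holds. Followed as written, SAP 7.4.3 gives the correct planned count for NKTR-255 and a wrong one for cetuximab. On the nominal schedule the cetuximab count is too low by a factor of 2 to 4 with the loading dose, or 1 to 3 without it, and about 3 for patients who stay on treatment. The ratios assume dosing on Days 1, 8 and 15 with no delays or skipped doses; individual values would differ otherwise.

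This is a minor point. It affects a descriptive row and its listing, and nothing in the visible text carries the number into an endpoint, a dose decision or another exposure variable.

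**What to change.** Define the variable by drug in SAP 7.4.3:

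- **NKTR-255:** keep the cycle number of the last non-zero dose.
- **Cetuximab:** one loading infusion plus all weekly infusions scheduled under the protocol from Cycle 1 Day 1 through the last non-zero cetuximab dose, excluding the period of single-agent NKTR-255 maintenance (protocol 5.2.4).

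Add that planned and actual infusions are counted on the same basis. The loading dose then enters both, and so does any weekly cetuximab scheduled during an NKTR-255 delay or after NKTR-255 is stopped and cetuximab continues alone.

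The cost is one or two sentences in the SAP and one derivation from dosing dates already collected. No new data are needed, and no dose, schedule or treatment rule changes.
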